10.4.1 Variable

The primary efficacy variable is the clinical benefit rate (CBR) (e.g. defined as CR, PR or SD) at week 24 by RECIST 1.1 for solid tumors and the Revised Response Criteria for Malignant Lymphoma, ([Cheson et al 2007](#)), for Lymphoma.

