14.3 Appendix 3: Eastern Cooperative Oncology Group (ECOG) performance status

Score	Performance status
0	Fully active, able to carry on all pre-disease performance without restriction.
1	Restricted in physically strenuous activity but ambulatory and able to carry out work of a light or sedentary nature, e.g. light housework, office work.
2	Ambulatory and capable of all self-care but unable to carry out any work activities. Up and about more than 50% of waking hours.
3	Capable of only limited self-care, confined to bed or chair more than 50% of waking hours.
4	Completely disabled. Cannot carry on any self-care. Totally confined to bed or chair.
5	Dead

14.4 Appendix 4: Adaptive Basket Trial for Combination Immune-therapy in Patients with Advanced Solid and Lymphoma

1 Introduction

This document outlines the adaptive design framework to be used for a single-arm Phase II study for the investigation combination immune-therapy across multiple cancer subtypes.

Seven pre-specified tumor cohorts, (also referred to as “groups”) are planned for the analysis:

Small-cell lung cancer (SCLC)	Gastroesophageal
Soft tissue sarcoma (STS)	Prostate
Ovarian	Advanced NET
Diffuse large B-cell lymphoma (DLBCL)	

The primary endpoint in each group is clinical benefit rate (CBR) assessed at 24 weeks. All patients will receive the experimental treatment.

The trial incorporates analyses based on a hierarchical model that allows for the possibility that the effect profile for the population of tumor types may be homogeneous or heterogeneous. There may be ‘clusters’ or subsets of tumor types – some in which the treatment is effective, and others not. The analysis borrows information, in a limited sense, from the tumor types that demonstrate similar CBR effects based on the trial data. The clustering used to characterize the distribution of tumor via a Dirichlet process prior (Escobar & West, 1995; Neal, 2000) is solely based on the observed CBRs. As described in Berry et al. [Berry, 2013], borrowing via a hierarchical model is a type of shrinkage estimation; it provides a formal mechanism by which extreme observations are shrunk toward the mean.

Prospectively, the model is developed by evaluating its performance from simulated trials. Hence, the false-positive rate can be controlled and power assessed. The advantages to borrowing are 1) increased precision of CBR estimates and 2) better decisions regarding CBRs.

2 Primary Analysis

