2.5.1 Primary endpoint

The primary endpoint is the clinical benefit rate (CBR) (e.g. defined as CR, PR or SD) at week 24 by RECIST 1.1 for solid tumors and the Revised Response Criteria for Malignant Lymphoma, (Cheson et al 2007), for Lymphoma.

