2.5.2 Statistical hypothesis, model, and method of analysis

The primary efficacy variable CBR is as defined below.

CBR at 24 weeks: CBR is defined as the proportion of patients with a best overall response of CR or PR or SD within the first 24 weeks of treatment.

In addition to tumor-specific measurements (e.g., radiological assessment of tumor response for solid tumors), progressive disease will also be considered when it was indicated either as a reason for the study treatment discontinuation or as a cause of on-treatment death. CR and PR (for solid tumors) require a confirmation that is at least a minimum of 4 weeks after the initial observation of response. Patients who had confirmed CR/PR or SD prior to or at 24 weeks, will be considered as achieving clinical benefit; patients who had confirmed CR/PR/SD prior to or at 24 weeks, but progressed at or after 24 weeks will also be considered as achieving clinical benefit.

CBR will be analyzed by comparing achieved CBR with a historical control rate of each tumor type, and if there is at least 80% probability that the response rate in a tumor type exceeds the historical rate, then the tumor type will be considered a success.

CBR will be analyzed, as mentioned below, by a Novartis designated vendor, [REDACTED].

The study will enroll patients from 7 tumor cohorts as mentioned in Section 1.1 study design.

We let Y_i be the response indicator for the i^{th} subject, and let R_g be the assumed probability of response within a control population and $\pi_g = \Pr(Y_i = 1 | g_i = g)$ be the underlying probability of response for group g within the trial. We transform to the logit scale for modeling purposes. Let θ_g be the mean log odds treatment effect, i.e.:

$$\theta_g = \log\left(\frac{\pi_g}{1 - \pi_g}\right) - \log\left(\frac{R_g}{1 - R_g}\right)$$

Thus, θ_g is the group specific logistic regression coefficient for group g . The primary analysis is a set of group specific tests that $\theta_g > 0$, meaning that the treatment is better than the assumed control rate for that group. Thus, we wish to test the set of hypotheses

$$H_{0g} : \theta_g \leq 0$$

$$H_{1g} : \theta_g > 0$$

We proceed in a Bayesian fashion, assigning a prior distribution (discussed below) and computing the posterior probability of H_{1g} within each group g . If, at the final analysis,

$$\Pr(\theta_g > 0 | \text{data}) > 0.80$$

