The final analysis will occur when both accrual and follow-up are complete for all groups. If, at the completion of the trial, there is at least 80% probability that the response rate in a group exceeds the historical rate, then the group will be considered a success. Formally:

$$\Pr(\pi_g > R_g) > 0.80.$$

In addition of above mentioned Bayesian analyses with all solid tumor types combined and separately for each hematological tumor type, the CBR estimate will be provided with its 95% exact CI. For tumor types (within the solid tumors) that have ten (10) or more patients, separate summaries will be performed by the tumor type and will also be displayed graphically. In the event that there are fewer than 4 patients for a hematological tumor type, only listing will be provided for that tumor type. In addition to summary by tumor types, separate summaries will also be provided by prior line of therapy and number of treatment cycles received.

CBR estimate with its 95% exact CI will also be provided for CBR by end of study using full analysis set. Additionally, for tumor cohort Prostate cancer an association of response(CBR) with PSA(prostate specific antigen) will be explored by summarizing the response at different level of PSA stratified by quartiles at baseline and 24 week.Similar analysis will also be repeated for ovarian cancer with Cancer Antigen-125 (CA-125).

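### SAP 2.5.2 defines the primary CBR as best response within 24 weeks, which conflicts with week-24 status elsewhere and is not comparable with the PFS-based benchmarks

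*SAP*

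**What the plan says.** Three places put the endpoint at week 24:

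- Protocol 10.4.1: "The primary efficacy variable is the clinical benefit rate (CBR) (e.g. defined as CR, PR or SD) at week 24".
- Protocol Appendix 4, Introduction: "The primary endpoint in each group is clinical benefit rate (CBR) assessed at 24 weeks".
- SAP 2.5.1: "clinical benefit rate (CBR) (e.g. defined as CR, PR or SD) at week 24 by RECIST 1.1 for solid tumors".

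SAP 2.5.2, which gives the working definition for the analysis, says something else. CBR is "the proportion of patients with a best overall response of CR or PR or SD within the first 24 weeks of treatment". It continues: "Patients who had confirmed CR/PR or SD prior to or at 24 weeks, will be considered as achieving clinical benefit". Patients with such a response are then covered by a further clause: those who had it "but progressed at or after 24 weeks will also be considered as achieving clinical benefit". It also states that "progressive disease will also be considered when it was indicated either as a reason for the study treatment discontinuation", or as the cause of an on-treatment death.

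SAP 2.5.3 lists who counts as a non-responder: patients with no valid assessment, an unconfirmed response, or an unknown or missing best response. Progression before week 24 is not on the list. SAP section 4 reports changes to the analysis sets only, and no change to the endpoint.

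**The concern.** For solid tumors, protocol Appendix 1 (14.1.17) gives a best response of SD for a single SD assessment more than 6 weeks after the start of treatment. The first on-treatment scan is at week 12 (protocol 7.2.1.1). A patient with SD at week 12 and PD at week 18 is therefore a success on the literal wording of SAP 2.5.2 and a failure under SAP 2.5.1 and protocol 10.4.1. For DLBCL, Appendix 2 has no best-response rule, so the point rests on SAP 2.5.2 alone.

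Each cohort succeeds if the posterior probability that its CBR exceeds the historical rate R_g is above 0.80, and the same probability drives futility and expansion. Appendix 4 (6.1.2) derives R_g from median PFS under an exponential model. If the observed rate is a more lenient quantity than the benchmark, an inactive drug can pass, and the false-positive rates in Appendix 4 Table 3 no longer describe the trial.

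**Working it through.** **Step 1. Reproduce the benchmarks.** Inputs are the median PFS values and R_g in Appendix 4 Table 1 (also protocol Table 10-1 and SAP Table 2-1). The documents do not state the time horizon. R_g = 0.5^(6/median in months) reproduces every row to within 0.04 points; for example, gastroesophageal is 0.5^(6/5) = 43.53% against 43.50% stated. R_g is therefore a 6-month progression-free rate.

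**Step 2. Rates for an inactive drug under the same model.** p(t) = 0.5^(t/median), with a month of 30.4375 days, so weeks 12, 18 and 24 are 2.76, 4.14 and 5.52 months.

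| Cohort | Median (mo) | R_g % | 0.5^(6/median) % | p(wk 12) % | p(wk 18) % | p(wk 24) % |
|---|---|---|---|---|---|---|
| SCLC | 1.5 | 6.25 | 6.25 | 27.9 | 14.8 | 7.8 |
| Gastroesophageal | 5 | 43.5 | 43.53 | 68.2 | 56.3 | 46.5 |
| STS | 6.2 | 51.1 | 51.13 | 73.5 | 63.0 | 54.0 |
| Prostate | 4 | 35.4 | 35.36 | 62.0 | 48.8 | 38.4 |
| Ovarian | 3 | 25.0 | 25.00 | 52.9 | 38.4 | 27.9 |
| Advanced NET | 5 | 43.5 | 43.53 | 68.2 | 56.3 | 46.5 |
| DLBCL | 3 | 25.0 | 25.00 | 52.9 | 38.4 | 27.9 |

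The week-12 rate for an inactive drug exceeds even the All Great target in Appendix 4 Table 2 in every cohort (11.84, 60.79, 67.79, 52.46, 40.16, 60.79, 40.16%).

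**Step 3. Chance of false success.** This uses n = 24 (the primary-population maximum in Appendix 4 section 3) and the exact binomial test at 0.20 that Appendix 4 section 8 uses for its independent analyses, taken as one-sided. The critical value r is the smallest count with P(X ≥ r | 24, R_g) ≤ 0.20. The remaining columns give P(X ≥ r | 24, p) for three readings:

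- (c) PD up to and including the week-24 scan is failure: p = p(wk 24).
- (b) PD before week 24 is failure, but PD on the week-24 scan is benefit: p = p(wk 18), an upper bound because it assumes that all progressions between weeks 18 and 24 are first seen on that scan.
- (a) Literal best response: p = p(wk 12), an upper bound because it assumes that every patient is scanned at week 12.

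| Cohort | r | True rate = R_g | (c) | (b), at most | (a), at most |
|---|---|---|---|---|---|
| SCLC | 3 | 18.7% | 28.7% | 70.9% | 98.0% |
| Gastroesophageal | 13 | 19.8% | 29.2% | 66.5% | 95.2% |
| STS | 15 | 18.1% | 26.4% | 60.8% | 92.2% |
| Prostate | 11 | 19.5% | 29.2% | 68.9% | 96.5% |
| Ovarian | 9 | 12.1% | 20.4% | 61.3% | 95.7% |
| Advanced NET | 13 | 19.8% | 29.2% | 66.5% | 95.2% |
| DLBCL | 9 | 12.1% | 20.4% | 61.3% | 95.7% |

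**Step 4. Relax the upper bounds.** The fractions below are assumptions, taken as independent of PFS.

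- (c) with 10% of progression-free patients lacking a valid scan and counted as failures, 0.9 × p(wk 24): 12-24%.
- (b) with a fraction f of the week 18-24 progressions recorded before the week-24 scan, p = p(wk 24) + (1 − f)[p(wk 18) − p(wk 24)]: f = 0.25 gives 51-62%, f = 0.50 gives 40-52%, f = 0.75 gives 30-41%. With f = 0.50 and 10% non-evaluable: 22-45%.
- (a) with 10, 20 or 30% non-evaluable: 73-96%, 44-93%, 19-88%.

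**Step 5. Who is misclassified under (a).** The share of patients scored as benefit who progress before week 24 is 1 − p(wk 24)/p(wk 12): 72% in SCLC and 27-47% in the other cohorts.

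**The case against.** Reading (a) is arguably not what was meant. SAP 2.5.2 labels the variable as CBR at 24 weeks. The clause about progression at or after week 24 would be redundant if earlier SD were enough whatever followed, and the sentence on PD as a reason for discontinuation would do little. The SAP refers the analysis details to Appendix 4, which assesses CBR at 24 weeks, and SAP 1.1.3 ties interim CBR data to patients who have completed 24 weeks of treatment. This stands as evidence of intent. It does not settle the matter: the preceding clause credits SD before week 24 without condition, no sentence makes early progression a failure, and the SAP says the Appendix 4 details are also in its own section 2.5. The stricter reading still credits PD first seen on the week-24 scan.

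Two other lines fit the best-response reading but prove little. One is the further estimate in SAP 2.5.2 ("CBR estimate with its 95% exact CI will also be provided for CBR by end of study using full analysis set"); the other is the inclusion in SAP 2.5.3 of confirmed responses up to the analysis cut-off, which may only allow for later confirmation.

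The calculation also omits the hierarchical model, the futility rules and the expansion gate. Its own baseline of 12-20% is above the 4.9-12.6% of the All Null column in Table 3. It shows direction and sensitivity to wording, not the trial's actual error rate. With 30% non-evaluable, reading (a) in STS gives 18.9%, close to the 18.1% baseline.

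**Conclusion.** The concern holds and must be fixed. SAP 2.5.2 conflicts with SAP 2.5.1, protocol 10.4.1 and Appendix 4, is ambiguous within itself, and leaves progression before week 24 unclassified for the variable that drives every cohort decision. Confidence is high for the textual conflict and for the mismatch with R_g.

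The size depends on the reading programmed, which the documents do not reveal: false success per cohort is 20-29% for week-24 status, at most 61-71% if PD on the week-24 scan is credited, and at most 92-98% for literal best response. These figures assume exponential PFS with the plan's medians, SD or better for every progression-free patient scanned, and independent tests at n = 24.

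Part of the excess in (c) over the 12-20% baseline has a separate, smaller cause: a 6-month benchmark is applied to a 24-week endpoint. The week-24 rate is 1.6 to 3.0 points above R_g (SCLC 7.8 − 6.25; prostate 38.4 − 35.4).

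**What to change.** In SAP 2.5.2, define CBR as no PD or death before the week-24 assessment and an overall response of CR, PR or SD at that assessment, within its window. Then:

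- Keep the rule that PD given as the reason for discontinuation or as the cause of an on-treatment death counts as PD.
- Delete the clause that makes SD before week 24 sufficient, and limit the last clause to progression after the week-24 assessment.
- State that a patient with no valid week-24 assessment is a non-responder, in line with SAP 2.5.3.
- Report the best-response figure and the end-of-study CBR only as disease control rates, not compared with R_g.
- Keep the prespecified R_g, and state that they are 6-month values and so somewhat lenient for a 24-week endpoint.
- In SAP section 4, record the clarification with its justification, and state which definition the interim decisions used.

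A separate, minor point works in the opposite direction: SAP 2.5.3 scores unconfirmed CR or PR as non-response for CBR, whereas under Appendix 1 such a patient has at least SD. The two should be reconciled.

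The cost is SAP wording, one response flag re-derived from scans already collected, and one rerun of the model if the flag changes. The observed CBR may fall. Because the SAP addendum already carries a post-database-lock entry and the trial is open-label, the reason for the change must be documented. Relative to the literal SAP 2.5.2 definition, this change of endpoint can only leave CBR unchanged or lower it.

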- PR = at least two determinations of PR or better at least 4 weeks apart before progression (and not qualifying for a CR) where confirmation required or one determination of PR prior to progression where confirmation not required
- SD = at least one SD assessment (or better) > 6 weeks after randomization/start of treatment (and not qualifying for CR or PR).
- PD = progression \leq 12 weeks after randomization/ start of treatment (and not qualifying for CR, PR or SD).
- UNK = all other cases (i.e. not qualifying for confirmed CR or PR and without SD after more than 6 weeks or early progression within the first 12 weeks)

Overall lesion responses of CR must stay the same until progression sets in, with the exception of a UNK status. A patient who had a CR cannot subsequently have a lower status other than a PD, e.g. PR or SD, as this would imply a progression based on one or more lesions reappearing, in which case the status would become a PD.

Once an overall lesion response of PR is observed (which may have to be a confirmed PR depending on the study) this assignment must stay the same or improve over time until progression sets in, with the exception of an UNK status. However, in studies where confirmation of response is required, if a patient has a single PR (\geq 30% reduction of tumor burden compared to baseline) at one assessment, followed by a <30% reduction from baseline at the next assessment (but not \geq 20% increase from previous smallest sum), the objective status at that assessment should be SD. Once a confirmed PR was seen, the overall lesion response should be considered PR (or UNK) until progression is documented or the lesions totally disappear in which case a CR assignment is applicable. In studies where confirmation of response is not required after a single PR the overall lesion response should still be considered PR (or UNK) until progression is documented or the lesion totally disappears in which case a CR assignment is applicable.

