6.1.2 Historical Control Rates

The assumed control CBRs (R_g) vary by group and are provided in the below table. Many of these rates are not directly available in the literature. Rather, we have estimated the CBR based on estimates of the median PFS time (and assuming exponential PFS). The median PFS times and estimated historical CBR rates are shown in Table 1. Because these rates vary, a numbering scheme (1 through 7) is used in simulations and corresponding results to index the 7 groups.

Group Index	Tumor Type	Median PFS (mo)	Hist. CBR (%)	Hypothetical Yearly Average Accrual (Subjects)
1	SCLC	1.5	6.25	20
2	Gastroesophageal	5	43.50	16
3	STS	6.2	51.10	13
4	Prostate	4	35.40	11
5	Ovarian	3	25.00	10
6	Advanced NET	5	43.50	7
7	DLBCL	3	25.00	6

Table 1 – Historical CBR for each group

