2.1.1.8 On-treatment assessment/event and observation periods

The overall observation period will be divided into three mutually exclusive segments:

1. *Pre-treatment period:* from day of patient's informed consent to the day before first administration of study drug
2. *On-treatment period:* from day of first administration of study drug to 30 days after last administration of study drug (Note: for ongoing patients, from day of first administration of study drug to the analysis cut-off date)
3. *Extended safety follow-up period:* from day 31 to at least day 150 after last administration of study drug or lost to follow-up.

In particular, summary tables for adverse events (AEs) will summarize only on-treatment events, with a start date during the on-treatment period, the so-called treatment-emergent AEs.

All safety data (including those from the pre-treatment and extended safety follow-up period) will be listed and those collected during the pre-treatment and extended safety follow-up period are to be flagged.

Additional summaries will be displayed to report deaths, all AEs, AEs related to study treatment, all SAEs and SAEs related to study treatment collected up to 150 days after last administration of study drug.

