- Progression Free Survival (PFS) defined as the time from the date of first dose to the date of first documented disease progression or relapse or death due to any cause during study medication or within 150 days from last dosing date, and is calculated as $PFS = (\text{date of progression/relapse or death} - \text{date of first study treatment} + 1)$. Disease progression noted as the reason for discontinuation of treatment will also be considered as a progression event for PFS analyses. If a patient has not had an event, progression free survival is censored at the date of last adequate tumor assessment
- Safety and tolerability based on number of incidences of AEs, SAEs, severe AEs, changes in laboratory parameters, vital signs and ECGs, drug interruption, reduction and dose intensity.

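### The SAP's CBR rule never makes death a failure, so some patients with a stable scan who die before week 24 are scored as clinical benefit

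*SAP*

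**What the plan says.** SAP 2.5.2 counts a patient as a success for "best overall response of CR or PR or SD within the first 24 weeks of treatment". It then adds: "Patients who had confirmed CR/PR or SD prior to or at 24 weeks, will be considered as achieving clinical benefit". A further clause says that responders or stable patients who "but progressed at or after 24 weeks will also be considered as achieving clinical benefit".

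Apart from scans, progression is recognised by two routes only. It "will also be considered when it was indicated either as a reason for the study treatment discontinuation or as a cause of on-treatment death". On-treatment is defined in SAP 2.1.1.8 as running "from day of first administration of study drug to 30 days after last administration of study drug".

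Protocol Appendix 1 (14.1.17) sets the bar for stable disease: "SD = at least one SD assessment (or better) > 6 weeks after randomization/start of treatment". The first scan is due at week 12, then weeks 18 and 24 (Protocol 7.2.1.1).

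SAP 2.5.3 makes non-responders of patients with no valid scan, with an unconfirmed CR or PR, or with an unknown or missing best response.

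SAP 2.5.1 and Protocol 10.4.1 word the same endpoint differently, as CR, PR or SD at week 24.

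For the historical rates R_g, Protocol Appendix 4, 6.1.2 says "we have estimated the CBR based on estimates of the median PFS time", assuming exponential PFS. The SAP's own PFS definition (2.7.1) includes progression "or death due to any cause during study medication or within 150 days from last dosing date".

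**The concern.** CBR is compared with a historical rate that is a progression-free survival probability. For the comparison to be fair, a patient who dies before week 24 should be a failure on both sides. The SAP's derivation rule mentions progression but not death, so a patient with one stable scan who then dies can keep SD as best response and count as a success.

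The error can only raise the observed CBR. It also means that a fatal toxicity of the combination can be scored as benefit in the endpoint that drives futility, expansion and final success. No supportive analysis of CBR is planned that would reveal it (Protocol 10.4.5 and SAP 2.5.4 both say not applicable).

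**Working it through.** **1. Which deaths before week 24 are caught?**

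| Patient | Rule that applies | CBR result |
|---|---|---|
| Dies with no valid scan, any cause | SAP 2.5.3 | Failure |
| Stops for progression, dies later | SAP 2.5.2, discontinuation route | Treated as progressed |
| Dies of progression within 30 days of last dose | SAP 2.5.2, on-treatment death route | Treated as progressed |
| SD at week 12, fatal toxicity at week 16 | None | Benefit |
| SD at week 12, stops for toxicity with last dose no later than week 13, no progression scan, dies of cancer at week 20 | None: (20 − 13) × 7 = 49 days after last dose, beyond 30 | Benefit |

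SAP 2.5.3 does not reach the last two rows, because a best response of SD is neither missing nor unknown, and SD needs no confirmation.

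**2. Is the timing feasible?** With a last dose at about week 12, day 31 after it falls at 12 + 31/7 = week 16.4. That leaves about 7.6 weeks before week 24 in which a cancer death is outside the on-treatment window. A non-progression death is missed at any time from the week-12 scan to week 24.

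**3. What are the historical rates?** Using R = 0.5^(6/median PFS in months) with the medians in Appendix 4, Table 1:

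| Group | Median (months) | Computed % | Stated % |
|---|---|---|---|
| SCLC | 1.5 | 6.25 | 6.25 |
| Gastroesophageal, NET | 5 | 43.53 | 43.50 |
| Sarcoma | 6.2 | 51.13 | 51.10 |
| Prostate | 4 | 35.36 | 35.40 |
| Ovarian, DLBCL | 3 | 25.00 | 25.00 |

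All seven agree to rounding, so R_g is 6-month PFS. Protocol Appendix 1 (14.1.19) and SAP 2.7.1 both count any-cause death as a PFS event.

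**4. How much could it matter?** Let d be the share of a cohort with a stable or better scan who die before week 24 outside every progression route. The documents give no value; 2% and 4% are assumed here. Take one cohort at the primary maximum of 24, with no borrowing and no interims. The cut-off r is the smallest count whose exact binomial tail at R_g is at most 0.20. A single-group version of the Bayesian model, with posterior above 0.80, gives the same r whether the 1.82 in the prior for μ is read as a variance or as a standard deviation. False success is P(Bin(24, R_g + d) ≥ r).

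| Group | r | d = 0 | d = 2% | d = 4% |
|---|---|---|---|---|
| SCLC | 3 | 0.187 | 0.318 | 0.452 |
| Gastroesophageal, NET | 13 | 0.198 | 0.258 | 0.326 |
| Sarcoma | 15 | 0.181 | 0.237 | 0.303 |
| Prostate | 11 | 0.195 | 0.257 | 0.327 |
| Ovarian, DLBCL | 9 | 0.121 | 0.175 | 0.239 |

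In SCLC the single-group posterior is about 0.58 at 2/24 and 0.81 to 0.82 at 3/24, so one misscored death can decide that cohort.

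**5. Set against the plan's own simulations.** Under the all-null scenario the adaptive design gives SCLC 0.049 with borrowing and 0.091 without (Appendix 4, Tables 3 and 17). The table in step 4 starts higher because it omits interim stopping and the expansion gate. The full clustered model was not rerun.

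**The case against.** The best counter-argument is that SAP 2.5.1 and Protocol 10.4.1 define CBR as status at week 24, which a patient dead at week 16 or 20 cannot meet. On that wording there is no gap. This stands as far as it goes: the problem comes from two conflicting endpoint definitions, and a reader should not infer that it would persist if week-24 status were enforced. But SAP 2.5.2 presents itself as the operative definition, and its timing clause speaks only of progression.

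A reader might also infer that every death fails only if it is on-treatment and due to progression. The documents do not support that. Deaths without a valid scan fail under SAP 2.5.3, and progression as the reason for stopping counts however late the death. The late cancer death is therefore a conditional case.

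It is also not secure that the SAP treats a toxic death as a PFS event. SAP 2.7.1 says any-cause death counts. SAP 2.7.3, read literally, censors a patient not known to have died of the underlying cancer. Nor do the documents show how the studies behind the median PFS values counted deaths.

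Finally, d is assumed. On the plan's exponential model, SCLC falls from 25% progression-free at 3 months to 6.25% at 6 months, a drop of 18.75 points. A d of 4% would need 4/18.75, about one in five, of those failures to be deaths outside every progression route. That is a fair reason to treat 4% as a high illustration for SCLC.

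**Conclusion.** The concern holds in this limited form. Under SAP 2.5.2 as written, two kinds of patient with SD at week 12 are scored as clinical benefit despite dying before week 24: those who die of a cause other than progression, and those who stopped for another reason, had no documented progression and died of cancer more than 30 days after the last dose. This contradicts the week-24 wording elsewhere and does not match an R_g computed as 6-month PFS. The mismatch with R_g assumes that the source studies counted any-cause death as an event.

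The direction favours the drug. The size is unknown, since it depends on d. The rise in SCLC from 0.19 to 0.32 or 0.45 shows how sensitive a low-rate cohort is; it is tempting to read these as the trial's false-success rates, but they come from a single cohort without borrowing or interims.

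The same best-response wording has a related weakness. Read literally, SD at week 12 followed by scan-documented progression at week 18 also leaves SD as best response; failure is only implied by the clause about progression at or after 24 weeks. A sentence on death alone would not repair the definition.

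**What to change.** In SAP 2.5.2, state that CBR requires the patient to be alive and progression-free with CR, PR or SD at the week-24 assessment. State also that death from any cause, or documented progression, before that assessment is a non-response regardless of time since the last dose. Apply the rule at the interims and at the final analysis.

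Align SAP 2.5.1, SAP 2.5.2 and Protocol 10.4.1 to this one definition, and reconcile the PFS death rule in SAP 2.7.1 with the censoring rule in SAP 2.7.3. The SAP's document history already lists changes made after database lock, so date and document this one and report CBR under both rules.

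The cost is a few sentences and a short derivation change, using death dates already collected on the Death eCRF page. CBR may come out slightly lower.
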